### 10.3. Other Safety Evaluations

#### 10.3.1. Columbia-Suicide Severity Rating Scale (C-SSRS)

The C-SSRS is a low-burden measure of the spectrum of suicidal ideation and behavior that was developed by Columbia University researchers for the National Institute of Mental Health Treatment of Adolescent Suicide Attempters Study to assess severity and track suicidal events through any treatment. It is a clinical interview providing a summary of both ideation and behavior that can be administered during any evaluation or risk assessment to identify the level and type of suicidality present. The C-SSRS can also be used during treatment to monitor for clinical worsening.i The C-SSRS evaluation will be performed as specified in the protocol Schedule of Assessments.

The C-SSRS has 11 binary (yes/no) outcomes corresponding to five categories of suicidal ideation, five categories of suicidal behavior, and the category of self-injurious behavior without suicidal intent:

Suicidal ideation is present if there is a “yes” response to any of the 5 suicidal ideation category questions. Suicidal behavior is present if there is a “yes” response to any of the 5 suicidal behavior category questions. Suicidal ideation or behavior is present if there is a “yes” response to any of the 10 suicidal or ideation or behavior category questions.

The number and percentage of patients with any post-baseline occurrence of the following ideations and behaviors will be presented overall, by study phase and treatment group:

- Suicidal ideation (overall and by individual question),
- Suicidal behavior (overall and by individual question),
- Suicidal ideation or behavior,

A similar tabulation of the occurrence of any of the above ideations and behaviors at baseline or as part of their lifetime history/past 12-month history (collected at the screening visit) will be presented overall, by study phase, and treatment group.

A shift table displaying the shift from worst pre-treatment category to the worst post-baseline category will be presented overall, by study phase, and treatment group. Best to worst C-SSRS category is defined in the following order: no suicidal ideation or behavior, suicidal ideation, and suicidal behavior. The worst post-baseline shift is calculated based on all post-baseline visits, including unscheduled visits. Worst pre-treatment will include all C-SSRS assessments prior to first dose date/time (screening or baseline). The denominator will be the number of patients with at least one non-missing baseline and post-baseline C-SSRS assessment.

Missing data will not be imputed.

Sponsor: Boston Pharmaceuticals, Inc.  
Protocol Number: BOS161721-02  
SAP Version and Date: Version 4.0, 23Apr2021

All C-SSRS individual items will be presented in data listings for screening and post-screening (since last visit), separately. A separate listing will be presented for patients with suicidal ideation, suicidal behavior, or non-suicidal self-injurious behavior for all randomized patients.

### 10.3.2. Vital Signs

Vital signs include: heart rate (beats/min); temperature (°C); systolic and diastolic blood pressure (mmHg). Observed values, changes, and percentage changes from baseline for vital signs will be summarized at each visit and time point, as well as for most extreme change overall, by study phase, and treatment group.

All vital signs data will be presented in patient data listings for all randomized patients.

### 10.3.3. 12-Lead Electrocardiogram (ECG)

ECG will be assessed as specified in the protocol Schedule of Assessments. The following ECG parameters will be collected: PR interval (msec), QRS interval (msec), RR interval (msec), QT interval (msec), and QT interval corrected for heart rate using Fridericia's formula (QTcF) (msec). ECG parameters and ECG evaluation will come directly from the database and will not be calculated during analysis.

Observed values, changes, and percentage changes from baseline for ECG parameters will be summarized at each visit, as well as for most extreme change overall, by study phase, and treatment group.

The number and percent of patients with the following parameters at any post-baseline visit and at each visit will be summarized:

- Abnormal, not clinically significant ECGs
- Abnormal, clinically significant ECGs

The number and percent of patients with each ECG evaluation result will be summarized by visit. The worst ECG evaluation at any post-baseline visit will also be summarized in the order of: Normal, Abnormal, not clinically significant, Abnormal, clinically significant.

For the summary of incidence at any post-baseline visit, the denominators for percentages will include patients with one or more non-missing value at any post-baseline visit. For the by-visit summaries, the denominators for percentages will include patients with a non-missing value at that visit.

Investigator reported ECG result shifts from baseline to each visit and worst case post-baseline will be summarized. Worst case post-baseline will be based on the most abnormal observed value on or after the randomization date.

Sponsor: Boston Pharmaceuticals, Inc.  
Protocol Number: BOS161721-02  
SAP Version and Date: Version 4.0, 23Apr2021

All ECG data will be presented in a by patient data listing for all randomized patients. A separate by patient listing for patients with abnormal, clinically significant 12-lead ECGs will also be provided in the safety analysis set for DMC meetings and the interim analysis only.

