## 5. GENERAL DATA HANDLING CONVENTIONS

## 5.1. Reference Dates

- Screening date is defined as the electronic case report form (eCRF) provided date on which a patient was screened for trial entry.
- Informed consent date is the date the patient signed the informed consent form.
- Randomization date is defined as the date on which the patient is randomized to study treatment.
- Treatment start date is defined as the date of first dose of study drug.
- Treatment end date is defined as the date of last dose of study drug.

- Age will not be calculated and will come directly from the eCRF. The eCRF uses the informed consent date as its reference date for age calculation.
- Safety data, such as AEs and laboratory assessments will use the treatment start date as a reference date.
- Efficacy data will use the randomization date as a reference date.
- Study day will be based on treatment start date as a reference date.

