## 5.4. Baseline, Post-Baseline Changes, and LOCF

Unless stated otherwise, baseline and post-baseline change values will be based on the following:

- Baseline will be based on the last non-missing value collected prior to or on the date/time of first dose of study drug.
- Post-baseline values will be those collected after the date/time of first dose of study drug.
- Change from baseline is defined as: value – baseline value.
- Percentage change from baseline is defined as:  $[(\text{value} - \text{baseline value}) / \text{baseline value}] * 100$ . Patients with baseline values of zero are excluded due to division by zero.
- Most extreme change: The maximum most extreme change will be the maximum post-baseline change value; the minimum most extreme change will be the smallest post-baseline change value. This calculation will consider all assessments collected after the first dose of study drug, scheduled or unscheduled.
- LOCF:
  - Imputation rules for assessments that include multiple components:
    - In case of missing laboratory components, lab values from the most recent unscheduled visit  $\leq 14$  days after the nominal visit will be utilized. If lab values are not available from an unscheduled visit  $\leq 14$  days after the visit, laboratory data will be carried forward from the most recent laboratory assessment  $\leq 30$  (scheduled or unscheduled) days prior to the nominal visit.
    - In case of missing non-laboratory components, no imputation will be performed.
  - In case of missing the entire score for an assessment, imputation will be based on LOCF. LOCF will only be implemented with the most recent prior visit (including unscheduled assessments). If the most recent prior visit is missing, occurred more than 30 days before (current visit date – most recent prior visit date  $> 30$ ), or is not evaluable, LOCF is not implemented. See Section 7 for further details. Additional details regarding LOCF for components for specific assessments are described in Section 7.
  - Observed values do not incorporate any imputations and are presented as collected.

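### The worst-case post-baseline ECG window in SAP Section 10.3.3 opens on the randomisation date, so it can overlap the baseline window

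*SAP*

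**What the plan says.** SAP V4.0, Section 10.3.3, plans the table as follows: "Investigator reported ECG result shifts from baseline to each visit and worst case post-baseline will be summarized". It then gives the worst case a window of its own: "Worst case post-baseline will be based on the most abnormal observed value on or after the randomization date".

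The general rules elsewhere in the SAP differ:

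- Section 5.4, baseline: "Baseline will be based on the last non-missing value collected prior to or on the date/time of first dose of study drug".
- Section 5.4, post-baseline: "Post-baseline values will be those collected after the date/time of first dose of study drug".
- Section 5.4 opens these rules with: "Unless stated otherwise, baseline and post-baseline change values will be based on the following".
- Section 5.1, safety: "Safety data, such as AEs and laboratory assessments will use the treatment start date as a reference date".
- Section 5.1, efficacy: "Efficacy data will use the randomization date as a reference date".

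The corticosteroid rules in Section 7.1.1 place randomisation on Day 0 and also identify Day 0 with the first dose. Section 10.3.3 leaves the timing of ECGs to the protocol's Schedule of Assessments.

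**The concern.** A shift table compares a value before treatment with a value after it, so the two windows must not share an observation. Section 10.3.3 opens the second window on a calendar date, and that date is also the day of first dose. An ECG recorded that day before the injection would satisfy both definitions. It would supply the baseline category and then compete again as a candidate for the worst post-baseline category.

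The rule also uses the anchor that Section 5.1 assigns to efficacy data, although ECG is a safety assessment. At stake is whether the worst-case part of the ECG shift table can be read at face value: an abnormality present before any drug was given could be reported as a post-baseline finding.

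**Working it through.** The plan gives no figure on this point, so the check sets the rules side by side and enumerates the table.

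**Step 1. The windows.**

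| Rule | SAP section | Cut point |
|---|---|---|
| Baseline | 5.4 | Up to and including date/time of first dose |
| Post-baseline (default) | 5.4 | After date/time of first dose |
| Most extreme change (also used for ECG intervals) | 5.4 | After first dose |
| C-SSRS worst pre-treatment | 10.3.1 | Before date/time of first dose |
| Worst-case post-baseline ECG | 10.3.3 | On or after randomisation date |

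On most extreme change, Section 5.4 is explicit: "This calculation will consider all assessments collected after the first dose of study drug, scheduled or unscheduled". Of these rules, only the worst-case ECG rule is tied to randomisation.

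**Step 2. The overlap.** Section 5.1 defines randomisation by date, with no clock time. Randomisation and first dose both fall on Day 0. An ECG on Day 0 before dosing is therefore at or before first dose (baseline window) and on or after the randomisation date (worst-case window). Whether such an ECG exists depends on the protocol schedule; I assume that it does. If the last pre-dose ECG is at screening, before the randomisation date, there is no overlap.

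**Step 3. The table.** Section 10.3.3 orders three results: normal (N), abnormal not clinically significant (NCS) and abnormal clinically significant (CS). Baseline by worst case gives 3 × 3 = 9 cells: 3 on the diagonal, 3 worsening and 3 improving.

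- Under Section 5.4: worst = max(post-dose values). All 9 cells can occur.
- Under Section 10.3.3, with the baseline ECG taken on Day 0: worst = max(baseline, post-dose values), which is never below baseline. NCS to N, CS to N and CS to NCS cannot occur, and their patients move to the diagonal. That leaves 9 − 3 = 6 cells.

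**Step 4. Individual patients.**

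| Day 0 pre-dose ECG | Post-dose ECGs | Section 10.3.3 gives | Section 5.4 gives |
|---|---|---|---|
| CS | All N | CS to CS | CS to N |
| CS | At least one CS | CS to CS | CS to CS |
| NCS | None recorded | NCS to NCS | No post-baseline value |
| CS, then repeat N before dosing | All N | N to CS | N to N |

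The last row is the only route to a false worsening. The repeat is the last pre-dose value and becomes baseline, while the earlier tracing stays inside the worst-case window. A single pre-dose ECG cannot produce it.

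**Step 5. Size.** Let p be the share of patients with an abnormal Day 0 pre-dose ECG, and q the fraction of them whose post-dose ECGs are all less abnormal than that tracing. The misclassified share is p × q. With q = 0 it is 0; with q = 1 it is p. The SAP gives neither quantity. For illustration only, assuming p = 25%, the range runs from 25% × 0 = 0% to 25% × 1 = 25%. Patients with no post-dose ECG come on top of this.

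**The case against.** The best defence is that the sentence defines a worst case *post-baseline*, and Section 5.4 already says what post-baseline means. Read together, a pre-dose tracing is baseline and cannot also be post-baseline. This does not rescue the text. The sentence states an explicit window of its own, and Section 5.4 applies only unless stated otherwise, so a programmer following Section 10.3.3 literally would include the Day 0 pre-dose ECG. Nor does permission to override cure an override that makes the two windows overlap.

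The second objection stands in full. The overlap needs a Day 0 pre-dose ECG, and the schedule is not shown. The wording is inconsistent in any case, but the consequences are conditional.

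Four stronger readings are tempting, and the SAP does not support them:

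- *Every patient with an abnormal Day 0 ECG is misclassified.* That is only the ceiling. Anyone with an equal or worse post-dose ECG lands in the same cell under either rule.
- *Normalisation is hidden.* It is lost only from the worst-case part. The same section plans shifts to each visit, results by visit and a full listing, where a return to normal remains visible.
- *Abnormal ECG counts are inflated throughout.* The summaries of abnormal and worst results at any post-baseline visit are visit-based and do not use this window. Interval parameters, including QTcF, use most extreme change, which is cut at first dose.
- *A baseline ECG is counted as on-treatment.* Section 5.3 defines on-treatment by date and includes the treatment start date, so a Day 0 tracing already belongs there. The term at issue is post-baseline.

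**Conclusion.** The point holds as a wording error with a limited, conditional effect. The worst-case ECG window conflicts with the post-baseline definition in Section 5.4 and with the safety reference date in Section 5.1. (Section 5.1 sets reference dates; it does not itself define post-baseline.)

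Given a Day 0 pre-dose ECG, the rule removes the improvement cells, assigns a worst post-baseline value to patients who have no post-dose tracing, and can disagree with the separate worst-result summary in the same section. A reader might infer that it routinely manufactures worsening. It does not: that needs an abnormal Day 0 pre-dose ECG followed by a normal pre-dose repeat, and nothing in the SAP shows that such repeats are taken.

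The misclassified share lies between none and the full share with an abnormal Day 0 ECG, and the SAP does not allow it to be narrowed. No efficacy analysis is affected. This is a minor point, worth correcting because safety is the primary endpoint of the Phase 1b portion (Section 7.1).

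**What to change.** In Section 10.3.3, replace the end of the sentence so that the worst case is *the most abnormal observed value collected after the date/time of first dose of study drug*, matching Section 5.4. Substituting the treatment start date (on or after) would not work, because that is also Day 0 and would still admit the pre-dose tracing.

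The programming of the worst-case shift table should apply the same date and time cut and leave out patients with no post-dose ECG. The cost is one phrase in the SAP and a check of one derivation; no new data are needed.

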#### 10.3.4. Physical Examinations

Targeted physical examination data and full physical examination data will be presented in patient data listings. A separate by patient listing for patients with abnormal, clinically significant physical examination findings will also be provided in the safety analysis set for DMC meetings and the interim analysis only.

### 11. CHANGES TO THE PLANNED ANALYSIS

The following changes were made to the planned analyses:

- Time to SRI-4 Response was originally a planned endpoint for the MAD and POC portions of the study. This was removed from the POC portion of the study upon Protocol Amendment 6 (30Apr2020); however, the endpoint was inadvertently maintained in the protocol for the MAD portion of the study. This analysis will not be performed for any study part.
- Rules for applying LOCF were vague within the protocol and were further detailed in this SAP. See Section 7 for further details.
- The PP was clarified to include additional criteria beyond the protocol description. The PP will exclude patients with more than one missed dose and missing both Day 180 and Day 210 efficacy assessments (BILAG, SLEDAI-2K, or PGA).
- Cytokine, chemokine and genotyping data were originally planned to be part of the MAD and POC portion of the study; however, data for these parameters is only available for the MAD portion of the study.
- The definition of the CLASI response in the protocol is vague as the protocol defines the CLASI response as 50% improvement from baseline in “A” (total activity) or “B” (total damage) scores. The SAP further clarifies the CLASI response as 50% improvement from baseline in CLASI and distinguishes a CLASI-A response from a CLASI-B response.

## 13. APPENDICES

### 13.1. COVID-19 Impact and Data Handling

The COVID-19 Pandemic resulted in contingency plans for BOS161721-02.

- **Safety Oversight:** In case a patient cannot return to the study site for the scheduled visit, the site staff will contact the patient remotely for safety follow up, for example, via telephone or video conferencing. The analysis of safety data will include all collected data regardless of remote data collection.
- **Central Laboratory:** In the case of courier issues that will prevent the protocol-required laboratory specimens to be sent to the study core laboratory, the site should have the safety laboratory specimens (Hematology, Chemistry, and Urinalysis) sent to their local laboratory for analysis and review by the study physician. The local laboratory data will not be entered into the clinical database or analyzed/presented in data summaries.
- **Investigational Product Dosing:** In cases when dosing cannot be performed during the protocol-designated windows, the Investigator should discuss each case with the Sponsor to determine whether it is a missed visit or whether the dosing can be performed outside protocol windows (as a protocol deviation). A minimum of 2 weeks must be maintained between consecutive doses. Patients who miss more than 2 doses of the study drug (whether consecutive or not) will be discontinued from the study and will undergo assessments as outlined in Section 5.5 of the study protocol (Premature Discontinuation). A sensitivity analysis of SRI-4 response using LOCF for missing data and/or observed case data may be performed to assess the impact of patients that did not follow the original protocol dosing schedule.

An addendum to this SAP will be developed that documents all additional data handling techniques employed to manage COVID impacted data, if needed, prior to database lock and unblinding.

[figure not shown]
Sponsor: Boston Pharmaceuticals, Inc.  
Protocol Number: BOS161721-02  
SAP Version and Date: Version 4.0, 23Apr2021

### 13.2. Physician's Global Assessment

Subject ID: \_\_\_\_\_ Patient Initials: \_\_\_\_\_ Date: \_\_\_\_/\_\_\_\_/\_\_\_\_ Visit: \_\_\_\_

### **PHYSICIAN'S GLOBAL ASSESSMENT (PGA)**

How do you assess your subject's current disease activity?

Result: \_\_\_\_\_ mm

Note: Please review the scale from previous visit, as applicable, and mark a vertical line on the scale above to assess the overall status of the subject's SLE signs and symptoms, and the functional capacity. Zero (0) = very good, asymptomatic and no limitation of normal activity; Three (3) = most severe possible disease ever seen in all SLE patients.

|                        |                   |      |
|------------------------|-------------------|------|
|                        |                   |      |
| Investigator Signature | Assessor Initials | Date |

### 13.3. SLEDAI-2K Index

|   |  |                        |  |
|---|--|------------------------|--|
| Subject Number: _____ - _____   |  |                        | Protocol BOS161721-02  |
| Screening / Randomization / _____ Week Visit & Date of Assessment: _____ - _____ - 20
(Circle visit type &/or enter visit week)                          |  |                        | (Day) _____ Month _____ Year _____   |
| SLEDAI 2K Index
Must be present at the time of visit or in the preceding 30 days (or 10 days for V1 and V2) and SLE-Related to be checked! |  |                        |  |
| Wt  | (  ) if Present | Descriptor             | Definitions
If descriptor is checked as present, please check appropriate condition(s) in definition and/or specify in the space provided.   |
| 8   |                            | Seizure                | Recent onset (last 28 days). Exclude metabolic, infectious or drug causes. Specify if checked:  |
| 8   |                            | Psychosis              | Altered ability to function in normal activity due to severe disturbance in the perception of reality. Include:  hallucinations,  incoherence,  marked loose associations,  impoverished thought content,  marked illogical thinking, and  bizarre, disorganized, or catatonic behavior. Exclude uremia and drug causes.   |
| 8   |                            | Organic Brain Syndrome | Altered mental function with  impaired orientation, memory or other intellectual function (with rapid onset and fluctuating clinical features),  inability to sustain attention to environment, and at least 2 of the following:  perceptual disturbance,  incoherent speech,  insomnia or daytime drowsiness,  increased or decreased psychomotor activity. Exclude metabolic, infectious or drug causes. |
| 8   |                            | Visual Disturbance     | Retinal changes of SLE. Include  cytoid bodies,  retinal hemorrhages,  serous exudate or hemorrhages in the choroid, and  optic neuritis. Exclude hypertension, infection, or drug causes.   |
| 8   |                            | Cranial Nerve Disorder | New onset of  sensory or  motor neuropathy involving cranial nerves.   |
| 8   |                            | Lupus Headache         | Severe, persistent headache. May be migrainous, but must be nonresponsive to narcotic analgesia. (Must have been severe enough to warrant lumbar puncture and/or MRI or head CT, perhaps hospitalization, and is thought to be due to active lupus cerebritis.) Specify if checked:   |
| 8   |                            | CVA                    | New onset of cerebrovascular accident(s) (CVA). Exclude arteriosclerosis. Specify if checked:   |
| 8   |                            | Vasculitis             |  Ulceration,  gangrene,  tender finger nodules,  periungual infarction,  splinter hemorrhages, or  biopsy or  angiogram proof of vasculitis.   |

Sponsor: Boston Pharmaceuticals, Inc.

[figure not shown]
Protocol Number: BOS161721-02

SAP Version and Date: Version 4.0, 23Apr2021

|   |                          |                       |   |
|---|--------------------------|-----------------------|---|
| Subject Number _____  |                          |                       | Protocol BOS161721-02   |
| Screening / Randomization / _____ Week Visit & Date of Assessment: _____ - 20
(Circle visit type &/or enter visit week) (Day) - (Month) - (Year) |                          |                       |   |
| 4   |  | Arthritis             | ≥ 2 joints with pain and signs of inflammation (  tenderness,  swelling or  effusion). (Complete Joint Count if checked.)                     |
| 4   |  | Myositis              | Proximal muscle aching/weakness associated with  elevated creatine phosphokinase (CK)/aldolase or  EMG changes or  a biopsy showing myositis. |
| 4   |  | Urinary Casts         | Heme-granular or red blood cell casts. (See labs)   |
| 4   |  | Hematuria             | >5 RBC/high power field. Exclude stone, infection, or other cause. (See labs)   |
| 4   |  | Proteinuria           | >0.5 gm/24-hour equivalent. (See labs)  |
| 4   |  | Pyuria                | >5 WBC/high power field. Exclude infection. (See labs)  |
| 2   |  | Rash                  | Inflammatory-type rash. Specify and complete CLASI if checked:  |
| 2   |  | Alopecia              |  Abnormal,  patchy or  diffuse loss of hair. (Complete CLASI if checked.)   |
| 2   |  | Mucosal Ulcers        |  Oral or  nasal ulcerations. (Complete CLASI if checked.)   |
| 2   |  | Pleurisy              | Pleuritic chest pain with  pleural rub or  effusion, or  pleural thickening.  |
| 2   |  | Pericarditis          | Pericardial pain with at least one (1) of the following:  rub or  effusion, or  ECG or  echocardiogram confirmation.  |
| 2   |  | Low Complement        | Decrease in CH50, C3 or C4 below the lower limit of normal for testing laboratory. (See labs)   |
| 2   |  | Increased DNA Binding | >25% binding by Farr assay or above normal range for testing laboratory. (See labs)   |
| 1   |  | Fever                 | >38°C (100.4F). Exclude infectious cause. Specify if checked:   |
| 1   |  | Thrombocytopenia      | <100,000 platelets/mm  (See labs)   |
| 1   |  | Leukopenia            | <3,000 white blood cells/mm  . Exclude drug causes. (See labs)  |
| TOTAL SCORE (Sum of all of weights next to descriptors marked present)  |                          |                       |   |
|   |                          |                       |   |
| Investigator Signature  |                          |                       | Date  |

